3 OBJECTIVES

[figure not shown]
3.1 Primary

- To compare PFS of subjects with newly-diagnosed MGMT-methylated or indeterminate GBM subtypes treated with RT plus TMZ combined with nivolumab or placebo. PFS will be determined by blinded independent central review (BICR) based on RANO criteria.
- To compare OS of subjects with newly-diagnosed MGMT-methylated or indeterminate GBM subtypes without baseline corticosteroids and regardless of baseline corticosteroids (ie, all comers) treated with RT plus TMZ combined with nivolumab or placebo.

3.2 Secondary

- To compare OS of subjects with newly-diagnosed MGMT-methylated or indeterminate GBM subtypes without baseline corticosteroids and regardless of baseline corticosteroids (ie, all comers) treated with RT plus TMZ combined with nivolumab or placebo at 12 and 24 months.
- To compare PFS based on investigator's assessment by RANO criteria of subjects with newly-diagnosed MGMT methylated or indeterminate GBM subtypes treated with RT plus TMZ combined with nivolumab or placebo.

4 ENDPOINTS

4.1 Primary Endpoint(s)

The primary endpoints of the trial will be assessed by OS and PFS.

[figure not shown]
OS is defined as time from the date of randomization to the date of death. Subjects who did not die by the end of the study will be censored to last known date alive. OS will be assessed in the randomized population with no corticosteroids at baseline and in the all randomized population.

PFS is defined as the time from randomization to the date of the first documented tumor progression or death due to any cause. Subjects who did not have disease progression or die will be censored at the date of the last tumor assessment. Subjects who did not have any on study tumor assessment and did not die will be censored at the last tumor assessment. Subjects who started any subsequent anti-cancer therapy without a prior reported progression will be censored at the last tumor assessment prior to initiation of the anti-cancer therapy. Subjects who had surgical resection after start of study treatment will be censored at the last tumor assessment date prior to initiation of surgical resection. PFS will be determined by BICR, based on RANO criteria. PFS will be assessed in the first 558 subjects from all randomized population. The progression free survival rate at time T is defined as the probability that a subject has not progressed and is alive at time T following randomization.

Censoring rules for the primary analysis of PFS are presented in [Figure 4.1-1](#). Alternate censoring rules for sensitivity analyses are specified in [Section 7.5.2.2](#).

[figure not shown]

[figure not shown]
Figure 4.1-1: Graphic Display of PFS Primary Definition

[figure not shown]

[figure not shown]
4.2 Secondary Endpoint(s)

[figure not shown]
- OS rate at 12 months and 24 months derived Kaplan-Meier curve of OS
- PFS assessed by investigator based on RANO criteria

[figure not shown]

[figure not shown]

5 SAMPLE SIZE AND POWER

This is a Phase 3, randomized, single blinded, multicenter study of RT+TMZ+nivolumab or placebo in adult (≥ 18 years) subjects with newly diagnosed GBM and MGMT-methylated or indeterminate tumors.

The familywise type I error rate for the primary comparisons will be set to 0.05, with 0.01 being allocated to the PFS comparison and 0.04 being allocated to the OS comparison.

The primary objectives on OS will test RT plus TMZ combined with nivolumab or placebo in the following hierarchy via a stratified log rank test:

1. OS in newly diagnosed MGMT-methylated or indeterminate GBM subtype without baseline corticosteroids.
2. If 1 is significant, OS in newly-diagnosed MGMT-methylated or indeterminate GBM subtype regardless of baseline steroid use (all comers).

The sample size for this study is based on the following assumptions:

- PFS and OS follows exponential distribution
- Median PFS in RT+TMZ arm is 10.0 months
- Hazard ratio (HR) of arm RT + TMZ + nivolumab vs RT + TMZ for PFS is 0.68, translated to median PFS improvement of 4.7 months (10.0 months vs 14.7 months for arm RT + TMZ and arm RT + TMZ + nivolumab, respectively)
- Median OS in RT+TMZ arm is 26.0 months³
- Hazard ratio (HR) of arm RT + TMZ + nivolumab vs RT + TMZ is 0.7 for the randomized population with no baseline corticosteroid, translated to median OS improvement of 11.1 months (26.0 months vs 37.1 months for arm RT + TMZ and arm RT + TMZ + nivolumab, respectively)
- Hazard ratio (HR) of arm RT + TMZ + nivolumab vs RT + TMZ is 0.75 for all randomized population, translated to median OS improvement of 8.7 months (26.0 months vs 34.7 months for arm RT + TMZ and arm RT + TMZ + nivolumab, respectively)

- Proportion of no baseline corticosteroid population within the entire newly-diagnosed MGMT-methylated or indeterminate GBM subtypes is 0.70

Approximately 693 subjects will be randomized in a 1:1 ratio, stratified by complete or partial resection. Of these 693 subjects, 485 subjects are assumed to be no baseline corticosteroids. Accrual is estimated to take approximately 25 months based on an observed monthly accrual in CA209548 of approximately 28 subjects per month; in the no baseline corticosteroids population, a piecewise accrual of 1, 4, 5, 8, 13, 16, 19, and then 23 subjects per month thereafter is assumed. At least 337 OS events (deaths) in the no baseline corticosteroid population are needed to achieve 88% power using a 2-sided Type 1 error of 4%. This number of events is projected to occur after an additional 44 months of follow-up (ie, at 69 months).

One interim analysis will be conducted on OS in the randomized population with no baseline corticosteroid. It will occur approximately 20 months after accrual is finished or when 70% or 236 OS events is reached which is estimated to occur at 45 months after study start, providing a 58% probability of stopping under H1. The stopping boundaries at the interim and final analyses will be based on the actual number of OS events at the time of the analysis using Lan-DeMets alpha spending function with O'Brien-Fleming boundaries. If the planned interim analyses occur exactly at the planned number of events, the projected alpha level will be 0.011 and 0.037. See [Table 5-1](#). The interim analysis will also be conducted on OS in the overall randomized population. The interim analysis will be conducted at the same time as the interim for the no baseline corticosteroids population in a hierarchy with stopping boundaries at the interim and final analysis based on actual number of OS events at the time of the analysis using Lan-DeMets alpha spending function with Pocock boundaries¹².

The PFS comparisons will be based on first 558 randomized subjects in all-comers. At least 404 PFS events are needed to achieve 90% power using a 2-sided Type 1 error of 1%. Accrual is estimated to take approximately 23 months and this number of events is projected to occur after an additional 12 months of follow-up (ie, at 35 months).

One interim analysis on PFS is planned and it will occur when 70% or 283 PFS events is reached, providing a 54% probability of stopping under H1, or when each of the 558 subjects reaches 12 months follow-up whichever comes first. The stopping boundaries at the interim and final analyses will be based on the actual number of PFS events at the time of the analysis using Lan-DeMets alpha spending function with O'Brien-Fleming boundaries. If the planned interim analyses occur exactly at the planned number of events, the projected alpha level will be 0.002 and 0.009.

Due to delayed BICR data, the number of PFS events passed the pre-specified events required for interim analysis and it was close to the number of pre-specified PFS events required for final analysis. As a result, interim analysis for PFS will not be conducted and alpha of 0.01 will be fully allocated to the final analysis for PFS.

Power calculations were done using East v 6.3 and R.

Table 5-1: Key Parameters of Sample Size Calculation of PFS and OS

Primary Endpoint	PFS	OS	OS
Power	90%	88%	87%
Alpha	0.01	0.04	0.04
Hypothesized Median Control vs. exp (months)	10 vs 14.7	26 vs 37.1	26 vs. 34.7
Hypothesized Hazard ratio	0.68	0.7	0.75
Expected number of events for comparison towards primary objective	404	337	494
Accrual Duration (months)	23	25	25
Sample size	558 (all-comers)	485 (no baseline corticosteroids)	693 (all-comers)
Expected number of events at IA		236	346
FPFV to IA (months)		45	45
FPFV to LPLV (months)	35	69	69

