
### **Statistical Considerations:**

**Sample Size:** Approximately 693 subjects will be randomized in a 1:1 ratio, stratified by complete or partial resection. Of these 693 subjects, 485 subjects are assumed to be considered as no baseline corticosteroids. Accrual is estimated to take approximately 25 months based on an observed monthly accrual in CA209548 of approximately 28 subjects per month; in the no baseline corticosteroids population, a piecewise accrual of 1, 4, 5, 8, 13, 16, 19, and then 23 subjects per month thereafter is assumed. At least 337 OS events in no baseline corticosteroid population are needed to achieve 88% power using a 2-sided Type 1 error of 4%. This number of events is projected to occur after an additional 44 months of follow-up (ie, at 69 months).

One interim analysis will be conducted on OS in the randomized population with no baseline corticosteroid. It will occur with approximately 70% or 236 OS events is reached. The stopping boundaries at the interim and final analyses will be based on the actual number of OS events at the time of the analysis, using Lan DeMets alpha spending function with O'Brien-Fleming boundaries. If the planned interim analyses occur exactly at the planned number of events, the projected alpha level will be 0.011 and 0.037. The interim analysis will also be conducted in OS in the overall randomized population. The interim analysis will be conducted at the same time as the interim for the no baseline corticosteroids population in a hierarchy with stopping boundaries at the interim and final analysis based on actual number of OS events at the time of the analysis using Lan-DeMets alpha spending function with O'Brien-Fleming boundaries.

The PFS comparisons will be based on first 558 randomized subjects in all-comers. At least 404 PFS events are needed to achieve 90% power using a 2-sided Type 1 error of 1%. Accrual is estimated to take approximately 23 months and this number of events is projected to occur after an additional 12 months of follow-up (ie, at 35 months).

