Approximately 693 subjects will be randomized in a 1:1 ratio, stratified by complete or partial resection. Of these 693 subjects, 485 subjects are assumed to be no baseline corticosteroids. Accrual is estimated to take approximately 25 months based on an observed monthly accrual in CA209548 of approximately 28 subjects per month; in the no baseline corticosteroids population, a piecewise accrual of 1, 4, 5, 8, 13, 16, 19, and then 23 subjects per month thereafter is assumed. At least 337 OS events (deaths) in the no baseline corticosteroid population are needed to achieve 88% power using a 2-sided Type 1 error of 4%. This number of events is projected to occur after an additional 44 months of follow-up (ie, at 69 months).

One interim analysis will be conducted on OS in the randomized population with no baseline corticosteroid. It will occur approximately 20 months after accrual is finished or when 70% or 236 OS events is reached which is estimated to occur at 45 months after study start, providing a 58% probability of stopping under H1. The stopping boundaries at the interim and final analyses will

be based on the actual number of OS events at the time of the analysis using Lan-DeMets alpha spending function with O'Brien-Fleming boundaries. If the planned interim analyses occur exactly at the planned number of events, the projected alpha level will be 0.011 and 0.037. See Table 8.1-1. The interim analysis will also be conducted on OS in the overall randomized population. The interim analysis will be conducted at the same time as the interim for the no baseline corticosteroids population in a hierarchy with stopping boundaries at the interim and final analysis based on actual number of OS events at the time of the analysis using Lan-DeMets alpha spending function with O'Brien-Fleming boundaries.

The PFS comparisons will be based on first 558 randomized subjects in all-comers. At least 404 PFS events are needed to achieve 90% power using a 2-sided Type 1 error of 1%. Accrual is estimated to take approximately 23 months and this number of events is projected to occur after an additional 12 months of follow-up (ie, at 35 months).

The technique of alpha-recycling will be used to adjust for multiplicity with details provided in the SAP.

Power calculations were done using East v 6.3 and R.

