#### **8.4.2.1 Analyses of Primary Endpoint**

The distribution of OS in the sub-population of subjects with no baseline corticosteroids and in all randomized subjects will be compared in arms RT + TMZ + nivolumab and RT + TMZ at interim and final analyses via two-sided, log-rank tests, stratified by complete resection or partial resection at baseline. The boundaries for declaring superiority at the interim and final analyses will be based on the actual number of OS events at the time of the analysis using Lan-DeMets alpha spending function with O'Brien-Fleming boundaries. For example, if the interim and final analyses occur exactly at the planned number of events, superiority of an arm will be declared if  $P \leq 0.011$  at the interim analysis or  $P \leq 0.037$  at the final analysis. The Kaplan-Meier product limit method will be used to estimate the survival curve in each arm including medians and its 95% CI, OS rates at various time points. The HR and the corresponding two-sided (1-adjusted  $\alpha$ ) % CIs will be estimated in a Cox proportional hazards model with treatment arm as a single covariate stratified by corresponding stratification factor (complete or partial surgical resection at baseline).

The comparison of PFS (by BICR) will be based on a two-sided log-rank test stratified by corresponding stratification factor (complete surgical or partial resection at baseline). PFS will be compared in the first 558 subjects out of the (total) 714 treated subjects. The Kaplan-Meier product limit method will be used to estimate the survival curve in each arm including medians and its 95% CI, PFS rates at various time points. The HR and the corresponding two-sided 99% CIs will

be estimated in a Cox proportional hazards model with treatment arm as a single covariate stratified by corresponding stratification factor (complete or partial surgical resection at baseline).

PFS (based on BICR) will be analyzed in overall randomized subjects and all randomized subjects without baseline corticosteroids.

The CA209548 DMC convened on 09-Dec-2020 to conduct a pre-planned, routine safety review of all data. Although the initial recommendation was that the study should continue unchanged and this was communicated to study investigators, subsequently the DMC notified BMS that they had deliberated further and unanimously agreed on the following:

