If the hypothesis cannot be rejected, then the study continues to proceed to the OS analysis. If, however, the hypothesis can be rejected, graph will be updated as per Algorithm 1 of Maurer and Bretz (2013), the algorithm ensures that in case PFS in the first 558 subjects from all randomized population is rejected, its entire alpha level (i.e., 0.01) is passed to OS in all randomized subjects without baseline corticosteroids. A simple hypothetical example is illustrated in Figure 7.5.4-2 and Figure 7.5.4-3.

Figure 7.5.4-2: Rejection of PFS in the First 558 Subjects from All Randomized Population

[figure not shown]

* first 558 subjects from all randomized population

** Nominal significance levels for based on O'Brien-Fleming with 70% observed information fraction

Further, if OS in all randomized subjects with no baseline corticosteroid is rejected, its significance level is passed to the OS in all randomizes subjects (see Figure 7.5.4-3).

Figure 7.5.4-3: Rejection of OS in All Randomized Population without Baseline Corticosteroids

** Nominal significance levels for based on O’Brien-Fleming with 70% observed information fraction

*** Nominal significance levels based on Pocock with 70% observed information fraction

Each time a hypothesis is rejected and the graph is updated, the alpha levels for IA and FA will be recalculated for each remaining OS endpoint using Lan-DeMets alpha spending function (O’Brien-Fleming boundaries will be used for OS in all randomized subjects without baseline corticosteroids, and Pocock boundaries will be used for OS in all randomized subjects). At the time of the final OS analysis, all events in the database at the time of the lock will be used.

Secondary endpoints are not included in a hierarchy of testing and, thus, these comparisons are not adjusted for multiplicity across endpoints. Analyses of the secondary OS and PFS endpoints (including p-values) will be performed for descriptive purpose only.

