7.5.5 Interim Analysis

An independent statistician external to BMS will perform the analysis. In addition to the formal planned interim analyses for PFS and OS, the DMC will meet at least every 6 months or more frequently as needed on an ad-hoc basis. Details are included in the DMC charter.

PFS

The population for PFS analysis is the first 558 randomized subjects. A formal interim analysis for superiority of PFS will be performed when approximately 283 (70% of planned events or 283/404) events is reached, or when the 558 subjects reach 12 months minimum follow-up, whichever comes first, where an event is either progression or death. The stopping boundaries at the interim and final analyses will be based on the actual number of PFS events at the time of the analysis using Lan-DeMets alpha spending function with O’Brien-Fleming boundaries. If the planned interim analyses occur exactly at the planned number of events, the projected alpha level will be 0.002 and 0.009.

Due to delayed BICR data, the number of PFS events passed the pre-specified events required for interim analysis and it was close to the number of pre-specified PFS events required for final analysis. As a result, interim analysis for PFS will not be conducted and alpha of 0.01 will be fully allocated to the final analysis for PFS.

OS

A formal interim analysis for superiority of OS is planned when 70% or 236 OS events is reached in the population of no baseline corticosteroids, which is estimated to occur at 45 months after study start. The stopping boundaries at the interim and final analyses will be based on the actual number of OS events at the time of the analysis using Lan-DeMets alpha spending function with O'Brien-Fleming boundaries to reject the null hypothesis of no treatment difference, controlling for a two-sided overall alpha of 4%. If the planned interim analyses occur exactly at the planned number of events, the projected alpha level will be 0.011 and 0.037.

OS in the all randomized subjects can be tested at the same time as the interim analysis of OS in the all randomized subjects without baseline corticosteroids and afterwards, provided analysis of OS in all randomized subjects without baseline corticosteroids is significant. The stopping boundaries at the interim and final analyses for all randomized subjects will be based on actual number of OS events at the time of the analysis using Lan-DeMets alpha spending function with Pocock boundaries.

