3.0	[REDACTED]	
[REDACTED]
 
Multiple editorial changes
 
Section 1: Research hypothesis and schedule of analyses are modified in accordance with the protocol update.
 
Section 2: Table 2.1-1 Study design schematic is modified in accordance with the protocol update.
 
Section 3: Objectives are modified in accordance with the protocol update.
 
Section 4: Primary and secondary endpoints are modified in accordance with the protocol update.
 
Section 5: Sample size considerations are modified in accordance with the protocol update.
 
[REDACTED]
 
Section 7.4: Analysis on TMZ by phase is removed.
 
Section 7.5.2: Statistical analysis on PFS is modified in accordance with the protocol update.
 
Section 7.5.3.4: Statistical analysis on treatment beyond progression is updated.
 
Section 7.5.4: Details on alpha recycling is added.
 
Section 7.5.5: Interim analysis is modified in accordance with the protocol update.
 
[REDACTED]

Table 10-1: Document History

Version Number	Author(s)	Description
		Multiple editorial changes
4.0	[REDACTED]	Section 1, Section 5 and Section 7.5.5 are updated on the change of removing interim analysis for PFS Section 2.5 is added. Section 4.3.7, Section 4.3.8 and Section 4.3.9 are updated on the analysis time window to be consistent with I-O core SAP. Section 7.5.3.2 is updated. Multiple editorial changes
5.0	[REDACTED]	Section 5: Replacing "O'Brien-Fleming" with "Pocock" in order to keep consistency with stopping boundary specified in sections 7.5.4 and 7.5.5 for all randomized population Section 7.5.4: Minor editorial changes on page 42 to add clarity Section 7.5.5: Minor editorial changes on page 43 to add clarity [REDACTED]

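### OS in all randomized subjects has an O'Brien-Fleming boundary in the protocol and a Pocock boundary in the SAP, and the SAP's 87% power fits only the former

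*SAP*

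**What the plan says.** **Protocol.** The Summary (Statistical Considerations) describes the interim and final boundaries for OS in the overall randomized population as "based on actual number of OS events at the time of the analysis using Lan-DeMets alpha spending function with O'Brien-Fleming boundaries". Section 8.1 repeats the rule for that population: "final analysis based on actual number of OS events at the time of the analysis using Lan-DeMets alpha spending function with O'Brien-Fleming boundaries". Section 8.4.2.1 says that OS "in the sub-population of subjects with no baseline corticosteroids and in all randomized subjects will be compared" and then gives a single O'Brien-Fleming rule for both populations, with example thresholds of 0.011 at the interim and 0.037 at the final analysis. Table 8.1-1 lists 87% power for all-comers OS.

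**SAP.** Section 5 uses the same spending framework, but "at the time of the analysis using Lan-DeMets alpha spending function with Pocock boundaries". Section 7.5.4 states that "Pocock boundaries will be used for OS in all randomized subjects", while O'Brien-Fleming applies to subjects without baseline corticosteroids. Section 7.5.5 again bases the all-comers boundaries on the "actual number of OS events at the time of the analysis using Lan-DeMets alpha spending function with Pocock boundaries". Table 5-1 carries the same 87% as the protocol table, with the same alpha, hazard ratio and event counts.

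The SAP's document history for version 5.0 records that the Section 5 wording was changed from O'Brien-Fleming to Pocock "in order to keep consistency with stopping boundary specified in sections 7.5.4 and 7.5.5 for all randomized population". It lists no change to Table 5-1.

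**The concern.** A confirmatory comparison needs one decision rule, fixed before the data are seen. Here a result could be significant under one document and not under the other, in either direction depending on the look. The power in SAP Table 5-1 also appears to have been carried over from the O'Brien-Fleming design. Pocock spending uses most of the alpha at the interim look and leaves a stricter final test, so at a fixed number of events its power should be lower.

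**Working it through.** **Inputs** (SAP Section 5 and Table 5-1; the protocol's figures are the same). All-comers OS: hazard ratio 0.75, 346 interim and 494 final events, 1:1 allocation, two-sided alpha 0.04 (0.02 per side). Information fraction t = 346/494 = 0.7004.

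**Formulas**
- Drift at d events: −ln(HR)·√d/2. This is 0.1438 × √346 = 2.676 at the interim and 0.1438 × √494 = 3.197 at the final analysis.
- O'Brien-Fleming-type interim spend, one-sided: 2 − 2Φ(z/√t), with z the upper 1% normal point.
- Pocock-type interim spend, one-sided: 0.02·ln(1 + (e − 1)t).
- The final critical value makes the total one-sided error 0.02 under a bivariate normal with correlation √t. Power comes from the same distribution shifted by the drifts.
- Critical hazard ratio: exp(−2z/√d), with z the critical value at that look.

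**Calibration on the plan's own figures.** For OS without baseline corticosteroids (236/337 events, HR 0.70, O'Brien-Fleming), the method gives nominal levels 0.0109 and 0.0367, a 57.7% chance of stopping at the interim and 88.5% power. The documents state 0.011, 0.037, 58% and 88%. The method reproduces the sponsor's design.

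**All-comers OS, both boundaries**

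| | O'Brien-Fleming (protocol) | Pocock (SAP) |
|---|---|---|
| Interim spend, one-sided | 0.00544 | 0.01580 |
| Critical z, interim / final | 2.546 / 2.090 | 2.149 / 2.347 |
| Nominal two-sided p, interim / final | 0.0109 / 0.0367 | 0.0316 / 0.0189 |
| Critical HR, interim / final | 0.760 / 0.829 | 0.794 / 0.810 |
| Chance of crossing at interim | 55.1% | 70.1% |
| Power | **86.9%** | **83.5%** |

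A fixed design with no interim look has power Φ(3.197 − 2.054) = 87.4%. The stated 87% therefore fits O'Brien-Fleming or a fixed design. It does not fit Pocock spending: 87 − 83.5 = 3.5 points.

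**Could another reading recover 87% under Pocock?**
- A classical Pocock boundary with equal levels (0.0257 at both looks) gives 85.1%. The SAP does not describe this.
- Passing the PFS alpha on, so that alpha is 0.05, gives 85.7%. Table 5-1 states 0.04.
- Freedman's drift instead of the one above lowers the Pocock figure to 82.9%.
- Reaching 87% with Pocock spending and a 70% interim would take about 544 events, against 494 planned.

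**Where the conclusions differ.** A final p-value between 0.0189 and 0.0367 succeeds under the protocol and fails under the SAP. An interim p-value between 0.0109 and 0.0316 does the reverse.

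**The case against.** The strongest reply is that no decision now depends on the boundary. After the unblinding of 22-Dec-2020, both documents say that OS in all randomized subjects will be presented descriptively. The OS analysis is no longer event-driven, more than 80% of the required events had been reached, and the gating hypothesis had conditional power below 1%. That is correct and limits the practical weight of the point. It does not remove the conflict, because SAP Sections 7.5.4 and 7.5.5 still describe a formal test and both documents still carry the rule.

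Second, the Pocock choice is deliberate, and Protocol 8.1 leaves the details of alpha recycling to the SAP. But Section 8.1 also names O'Brien-Fleming outright for this comparison, so the deferral does not reconcile the texts.

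Third, 87% is a carried-over design figure, correct for the protocol's boundary, and the required event number is tied in the text to subjects without baseline corticosteroids. No sample size would change. This stands: the fault is a table cell left unrevised when the boundary wording changed.

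Fourth, all-comers OS is tested only if OS without baseline corticosteroids succeeds, so neither 87% nor 83.5% is the power of the full procedure. This also stands. Simulating the gate requires assuming that the remaining 157 events (494 − 337) carry the hazard ratio implied by the two stated ones, about 0.87. If all-comers testing may continue to the final analysis, power is about 83% with O'Brien-Fleming and 80% with Pocock. If the trial stops once the first hypothesis succeeds at the interim, it is about 74% and 77%, so the order reverses. The tables, however, quote marginal powers, and a marginal figure is the like-for-like replacement.

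**Conclusion.** The concern holds on both counts. The protocol and SAP specify different boundaries for the same primary comparison, and Table 5-1's 87% is about 3.5 points above the 83.5% that the SAP's boundary delivers. Protocol Table 8.1-1's 87% is right for the protocol's own boundary.

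The 83.5% rests on the Lan-DeMets Pocock-type spending function as the SAP words it, looks at exactly 346 and 494 events, alpha 0.04, proportional hazards at 0.75, and no allowance for the gate. Type I error is not at risk under either boundary, provided one is fixed in advance. The point should be corrected because the documents govern a primary hypothesis, but its effect on the trial's conclusions is small.

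**What to change.** State one spending function for OS in all randomized subjects in both documents.

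- **If Pocock stays:** amend the protocol Summary and Sections 8.1 and 8.4.2.1, and restate the all-comers power in Protocol Table 8.1-1 and SAP Table 5-1 as about 83%.
- **If O'Brien-Fleming stays:** restore it in SAP Sections 5, 7.5.4 (including the Figure 7.5.4-3 footnote) and 7.5.5, and keep 87%.

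In either case, a short table note should say that the power is marginal and ignores the gate through OS without baseline corticosteroids. The cost is wording and at most one restated figure, with no further subjects, follow-up or data.
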